9.4.3 Main Analytical Approach

Percentage change from baseline in PASI score at each visit will be summarised. Mean (+/- SD) percentage change from Baseline over time will be plotted in a figure. Also, waterfall plots will be created to show the ranked individual percentage change from Baseline at Week 16.

The primary analysis will be performed using a Bayesian mixed model for repeated measures (MMRM). The model will include parameters for treatment*visit and baseline PASI score*visit interactions and will not include an intercept.

Treatment will consist of 4 levels (all placebo, EDP1815 1 capsule, EDP1815 4 capsules and EDP1815 10 capsules) if the placebo pooling strategy is considered appropriate or 6 levels (Placebo 1 capsule, Placebo 4 capsules, Placebo 10 capsules, EDP1815 1 capsule, EDP1815 4 capsules, and EDP1815 10

capsules) if the placebo pooling strategy is not considered appropriate. Visit will consist of 7 levels (Weeks 1, 2, 4, 8, 12,16 and 20).

As described in [Section 9.2](#) additional covariates for baseline factors will be assessed using this model for inclusion in all efficacy models.

The priors for all parameters in the model will be non-informative and follow a normal distribution with mean 0 and SD 1000. The prior for the variance-covariance matrix will follow an inverted Wishart distribution with degrees of freedom equal to the number of visits and an identity scale matrix. The choice of Wishart distribution is based on it being the conjugate prior of the inverse-covariance matrix of a multivariate-normal random vector.

The model will be blocked so that the MCMC procedure samples from the treatment*visit parameters first, then the baseline*visit parameters, then any additional fitted covariates and finally the variance-covariance matrix.

100,000 MCMC samples will be generated with a thin of 20 to leave 5000 retained samples after a burn-in of 10,000 samples. The number of samples or thin may be increased to reduce the ratio of the Monte Carlo standard error (MCSE) to the posterior SD, as deemed necessary.

If the assumption of similarity between the 3 placebo cohorts is considered appropriate, the placebo cohorts will be pooled, and a common all placebo control group will be used for the pairwise differences or each active dose to placebo. If the placebo pooling strategy is not considered appropriate, each placebo dose will be included in the model as a separate dose level and pairwise comparisons between each active EDP1815 dose and its matching placebo dose will be used.

The adjusted mean percentage change from baseline and the associated 95% highest posterior density (HPD) credible interval (Crl) for each treatment group at Week 16 will be reported, together with the adjusted mean difference from placebo and the associated 95% HPD Crl for each active dose at Week 16 and the probability that each active treatment difference is less than 0%, -20%, -30% and -50%.

At all other visits (Weeks 1, 2, 4, 8, 12 and 20) the adjusted mean percentage change from baseline and the associated 95% highest posterior density (HPD) credible interval (Crl) for each treatment group will be reported, together with the adjusted mean difference from placebo and the associated 95% HPD Crl for each active dose and the probability that each active treatment difference is less than 0%.

Posterior mean (with 95% HPD Crl) percentage change from baseline in PASI score will be plotted against time.

Model checking and diagnostic plots, including posterior density plots of the posterior samples for all parameters in the model will be produced. The assumption that data are missing at random will be evaluated by plotting the mean percentage change in PASI score against visit by treatment group for

the subgroups of participants who completed 16 weeks of study drug compared with those who discontinued study drug before Week 16.

If model checking and diagnostic plots show a violation of the assumptions underlying the analysis, alternative statistical methods will be considered, appropriate to the type of violation observed. This may include removing additional covariates even if they are found to be statistically significant if their inclusion causes issues with model inclusion, using an appropriate transformation (e.g. logarithmic) on the endpoint or changing the modelling strategy from MMRM. Requirements for alternative methods will be data driven and cannot be fully assessed until after the study has been unblinded and this document finalised. Any changes to the modelling strategy will be fully described in a SAP addendum.

The primary analysis approach will be repeated using the 3 supportive estimands described in [Section 9.4.2](#).

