6.4.3.4 Analysis of Fecal Microbiome

The microbiome composition of stool samples will be assessed by 16S ribosomal RNA sequencing, which looks at the diversity and abundance of microbes in the colonic microbiome (Human Microbiome Project Consortium 2012). EDP1815 is not expected to alter the composition of the microbiome, but it is being evaluated as a safety biomarker.

7 Statistical Considerations

Analysis methods for key endpoints are described below. Further details on all analyses will be described in the SAP.

No formal hypothesis will be tested. A model-based probability inference approach in a Bayesian framework will be used to guide decision-making around dose selection. Posterior estimates and 95% CrI for the difference between each active dose and placebo will be produced for relevant primary and secondary endpoints.

Unless otherwise specified, missing data will be considered as missing at random and will be accounted for using mixed models for repeated measures, with all time points collected for the relevant endpoint included in the model. This includes data which is excluded due to collection after treatment discontinuation or after a protocol deviation as applicable to the definition of the estimands used in the analysis.

The primary analysis for the study will occur after all participants have completed 4 weeks of follow-up after their last dose of study medication (end of Part A). The final analysis for the study will occur when all participants have completed the required relapse and rebound follow-up period of up to 24 weeks post-treatment (end of Part B).

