7.1 Estimands and Intercurrent Events

7.1.1 Primary Efficacy Estimand

The primary estimand will be the effect of EDP1815 on the percent change in PASI score from baseline to Week 16 in the mITT set of all treated participants, regardless of deviations from the protocol. Only data collected while on treatment will be used to account for the intercurrent event of treatment discontinuation (hypothetical strategy based on adherence to treatment only). The posterior mean difference between each active dose and the pooled placebo will be estimated.

Percent change from baseline in PASI score at each visit will be calculated as:

$$100 * (\text{PASI score at Visit} - \text{baseline PASI score}) / \text{baseline PASI score}.$$

A negative percentage change from baseline will indicate an improvement.

For the primary analysis, 3 supportive estimands will also be considered:

- To assess the impact of intercurrent events related to protocol deviations believed to impact efficacy, a supportive analysis will be performed where all data collected after any such identified protocol deviations will be excluded. Participants who had a protocol deviation believed to impact efficacy prior to the first dose of treatment (hypothetical strategy based on adherence to treatment and the aspects of the protocol which impact efficacy) will be completely excluded from this analysis.
- To assess the impact of treatment discontinuation for any reason, a supportive analysis will be performed in which all data collected up to the end of Week 16, including any data collected after treatment discontinuation will be included (treatment policy strategy).
- To assess the impact of treatment discontinuation due to a requirement for alternative therapy, a supportive analysis will be performed where the highest PASI score recorded prior to treatment discontinuation will be applied to all expected visits after treatment discontinuation up to Week 16.

The primary analysis will be performed using a Bayesian MMRM as fully described in Section 7.6.1. Data from visits prior to Week 16 will be included in the model and missing data will not be explicitly imputed.

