7.6.1 Analysis of Primary Efficacy Endpoint

The assumption that the 3 cohorts of placebo participants can be pooled into a single placebo group to be used as a control for all active doses will be examined using mean ($\pm \text{SD}$) plots and box plots of percent change in PASI score against time. In addition, an MMRM will be used to compare the 3 cohorts of placebo participants. The model will include parameters for cohort, visit and baseline PASI score together with cohort*visit and baseline PASI score*visit interactions. Least squares mean (95% CI) estimates for each placebo cohort will be plotted by visit.

A decision will be made by the Evelo study team, based on examination of the above figures and model, on whether the pooling strategy is appropriate.

The primary analysis will be performed using a Bayesian MMRM. The model will include parameters for treatment*visit and baseline PASI score*visit interactions. Body mass index, gender, country, and time since diagnosis will also be considered and included as parameters if found to be significant ($p < 0.05$). The model will not include an intercept. Visit will consist of 6 levels (Weeks 1, 2, 4, 8, 12, and 16) and treatment will consist of 4 levels (pooled placebo, EDP1815 0.8×10^{11} cells, EDP1815 3.2×10^{11} cells, and EDP1815 8.0×10^{11} cells) if the placebo pooling strategy is considered appropriate or 6 levels (Placebo matching EDP1815 0.8×10^{11} cells, Placebo matching EDP1815 3.2×10^{11} cells, Placebo matching EDP1815 8.0×10^{11} cells, EDP1815 0.8×10^{11} cells, EDP1815 3.2×10^{11} cells, and EDP1815 8.0×10^{11} cells) if the placebo pooling strategy is not considered appropriate.

The priors for all parameters in the model will be non-informative and follow a normal distribution with mean 0 and SD 1000. The prior for the variance-covariance matrix will follow an inverted Wishart distribution with degrees of freedom equal to the number of visits and an identity scale matrix. The choice of Wishart distribution is based on it being the conjugate prior of the inverse-covariance matrix of a multivariate-normal random vector.

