7.7 Visit Windows

All data will be reported according to nominal visits, except for subjects who complete the follow-up Week 20 assessments due to withdrawing from the study before the Week 16 visit. For example, if a Week 2 visit occurred on Day 16 instead of the nominally expected Day 14 it will be reported and included in the summary statistics/statistical analyses for Week 2.

Subjects who withdraw prematurely from the study should complete the assessments required for the follow-up visit (Week 20). However, this data will only be included in tables and figures which are produced **by visit** for subjects who completed the 16-week treatment period and provided Week 16 data prior to the Week 20/follow-up data being collected. Tables and figures which do not show summaries by visit and all listings will include all collected Week 20/follow-up data regardless of whether the subject completed the 16-week treatment period.

Scheduled visits which occur outside the protocol-specified visit window (e.g. if the Week 2 visit occurred on Day 19 outside of the Day 12-18 window), this will be noted as a protocol deviation but data collected will still be included in all summary and analysis tables.

Unscheduled visits will not be included in summary or analysis tables, unless they are baseline measurements or provide data towards a safety endpoint which looks at worst-case post-baseline.

8 Summary of Study Data

All continuous variables will be summarized using the following descriptive statistics: n (non-missing sample size), mean, SD, median, maximum and minimum. The frequency and percentages (based on the non-missing sample size) of observed levels will be reported for all categorical measures.

In general, all data will be listed, sorted by randomized treatment (Placebo, EDP1815), cohort (1, 2, 3), site number and participant number. Relevant listings will include whether the assessment was performed and the date, study day/visit and time of the assessment as applicable.

Unless otherwise specified below, all summary tables will be structured with a column for each treatment. Where appropriate, columns combining all placebo participants, all EDP1815 participants and an overall total column may also be presented.

For summaries of study disposition, demographic and baseline data and study treatment compliance, columns will be ordered and labelled as follows:

- Placebo 1 capsule
- EDP1815 1 capsule
- Placebo 4 capsules
- EDP1815 4 capsules

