9.4 Primary Efficacy Analysis

9.4.1 Primary Efficacy Estimand

The primary efficacy estimand will be the effect of EDP1815 compared to placebo on the percentage change from baseline to Week 16 in PASI score. The population summary measure of interest will be the difference in mean percentage change from baseline in PASI score at Week 16.

Intercurrent events will be accounted for in the following manner:

Table 3 Intercurrent Event Strategies for the Primary Estimand

Intercurrent event	Strategy to account for intercurrent event
Protocol deviation with potential to impact efficacy	Treatment policy PASI scores will be used as collected regardless of whether a protocol deviation occurred
Treatment discontinuation for any reason *	While on treatment PASI scores collected more than 4 days after treatment discontinuation will be considered as missing for all timepoints up to Week 16. For the Week 20/follow-up visit, PASI scores will be considered as missing for subjects who did not complete treatment up to Week 16.

* This includes participants who completed the 16-week treatment period but have their Week 16 visit more than 4 days after the end of treatment.

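### The SAP's primary model adds off-drug Week 20 without declaring it, and two SAP rules disagree on late Week 16 PASI scores; the likely numerical effect is small

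*SAP*

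**What the plan says.** **Visits in the primary model.** Protocol 7.6.1: "Visit will consist of 6 levels (Weeks 1, 2, 4, 8, 12, and 16". SAP 9.4.3: "Visit will consist of 7 levels (Weeks 1, 2, 4, 8, 12,16 and 20". The list of departures from the protocol (SAP Section 13, Table 8) has four entries, and this is not one of them.

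**Data used for the primary estimand.** Protocol 7.1.1: "Only data collected while on treatment will be used to account for the intercurrent event of treatment discontinuation". Even the protocol's treatment-policy supportive estimand stops at the end of Week 16.

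**Late Week 16 scores.** SAP Table 3 (9.4.1): "PASI scores collected more than 4 days after treatment discontinuation will be considered as missing for all timepoints up to Week 16". Its footnote extends this to completers: "This includes participants who completed the 16-week treatment period but have their Week 16 visit more than 4 days after the end of treatment". SAP 7.7 says of scheduled visits outside the protocol window that "data collected will still be included in all summary and analysis tables".

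**Week 20 scores.** SAP Table 3: "For the Week 20/follow-up visit, PASI scores will be considered as missing for subjects who did not complete treatment up to Week 16". Completers keep theirs, including those whose Week 16 score has been set to missing.

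**The concern.** There are two separate problems.

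First, the fitted primary model is not the one in the protocol. It takes in a visit that is off drug by design, and the SAP does not say that this is a change. Week 20 also enters the covariate selection in SAP 9.2, because the stepwise search runs in this same model and its result is carried into the other models with covariates.

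Second, the SAP gives two answers on whether a late Week 16 score counts, so two programmers could build different primary data sets. Under Table 3 the outcome is also uneven: a score 5 days off drug is rejected as off-treatment, while the same person's score about 4 weeks off drug stays in the model and helps to predict the value that was removed.

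**Working it through.** **1. Scale, from the plan's own figures.** Protocol 7.3 and SAP Section 6 give a difference of 20 points, SD 25, and 42 active and 21 placebo evaluable per cohort (63 pooled placebo). The 5% level is taken as two-sided.

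- Pooled: SE = 25 × √(1/42 + 1/63) = 4.98; 20/4.98 − 1.96 = 2.06; power 98.0% (plan: more than 95%).
- Within cohort: SE = 25 × √(1/42 + 1/21) = 6.68; 20/6.68 − 1.96 = 1.03; power 84.9% (plan: more than 80%).

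Both stated figures hold. The yardstick is a 20-point effect with an SE near 5.

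**2. Where the two rules meet.** SAP 5.3.4.2 ends treatment for completers on Day 112. Protocol Table 6-1 gives windows of Days 110–116 (Week 16) and 141–148 (Week 20).

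- 116 − 112 = 4 days, so with a Day 112 last dose Table 3 starts to remove scores at Day 117, the first day past the window. SAP 7.7 keeps those visits.
- Week 20 is 141 − 112 = 29 to 148 − 112 = 36 days after that dose.

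**3. Weight of Week 20 in predicting a missing Week 16.** The documents give no correlation, so two structures are assumed, each over a range.

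- AR(1) with 4-week correlation r. Week 16 lies midway between Weeks 12 and 20, so each gets r/(1 + r²): 0.40 at r = 0.5 and 0.50 at r = 0.9.
- Compound symmetry with correlation ρ. Each of the six other visits gets ρ/(1 + 5ρ): 0.14 at ρ = 0.5 and 0.16 at ρ = 0.9. Weeks 1–12 together carry 0.71 to 0.82.

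The weight applies to a person's deviation from the mean of their own arm at Week 20, because the model contains treatment*visit. An average loss of effect after stopping is absorbed there.

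**4. Effect on the Week 16 contrast.** Early discontinuers are not affected by adding Week 20, because Table 3 sets their Week 20 to missing too. For late completers, take an adverse case in which those in one arm are 10 points worse at Week 20 than the model expects. The shift is about (share late) × (weight) × 10:

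| Structure | Weight | 5% late | 10% late |
|---|---|---|---|
| Compound symmetry, ρ = 0.5 | 0.143 | 0.07 | 0.14 |
| Compound symmetry, ρ = 0.9 | 0.164 | 0.08 | 0.16 |
| AR(1), r = 0.5 | 0.400 | 0.20 | 0.40 |
| AR(1), r = 0.9 | 0.497 | 0.25 | 0.50 |

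A simulation (42 v 63, known covariance, 600 runs per setting, the active arm losing 12 of its 20 points by Week 20) gave these changes from six to seven visits:

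| Late share | AR(1) 0.8, lateness unrelated to outcome | CS 0.7, unrelated | AR(1) 0.8, 10 points worse | CS 0.7, 10 points worse |
|---|---|---|---|---|
| 0% | 0.00 | 0.00 | 0.00 | 0.00 |
| 5% | −0.01 | −0.01 | 0.25 | 0.08 |
| 10% | 0.03 | 0.00 | 0.47 | 0.16 |

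With lateness unrelated to outcome, the run-to-run SD of the change was 0.10 to 0.61 points.

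**5. Precision.** SE of the Week 16 contrast by GLS (50 v 75, 15% dropout, Week 16 SD 25, assumed correlation 0.95 per week). With all Week 16 scores kept it is 4.81.

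| Completers losing Week 16 | Six visits | Seven visits | Ratio |
|---|---|---|---|
| 5% | 4.85 | 4.83 | 1.004 |
| 10% | 4.90 | 4.86 | 1.008 |
| 20% | 5.02 | 4.93 | 1.018 |

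**The case against.** The best defence is that little follows numerically and that much of this looks deliberate. SAP 9.4.3 reports Week 20 contrasts from this model, and Table 3 gives Week 20 a rule of its own. Seven visits are slightly more precise. The opening of protocol Section 7 describes mixed models "with all time points collected for the relevant endpoint included in the model". Removing late Week 16 scores fits the protocol's on-treatment principle, and SAP Supportive Estimand 2 keeps them. The Table 3 footnote addresses late Week 16 visits specifically and would naturally override the general rule in 7.7. The two rules also overlap only in part: Table 3 counts from the end of treatment and 7.7 from study day, so someone still dosing close to a Day 118 visit is out of window but kept by both.

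Most of this stands as a limit on the size of the problem. It does not remove the problem. The general sentence in protocol Section 7 yields wherever something else is specified, and 7.6.1 specifies six visits. SAP 7.7 contains no exception that points to Table 3.

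A reader might infer more: that off-drug data stand in for the primary endpoint, or that washout differing by arm flows into the Week 16 estimate. The documents do not support either. SAP 7.3 imputes nothing here; Week 16 stays missing, and Week 20 informs it only alongside the earlier visits. Treatment*visit takes up each arm's average washout. In a separate simulation in which the active arm alone lost 15 points at Week 20, with 5%, 10% and 20% of completers losing Week 16 at random, the contrast moved by 0.003, 0.004 and 0.05 points.

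**Conclusion.** The point holds as an undeclared departure from the protocol's primary model and a conflict between two SAP rules on late Week 16 scores. The target remains the Week 16 difference.

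The expected shift is near 0 if lateness is unrelated to outcome. It is 0.07 to 0.50 points in the adverse case with 5% to 10% late, against a 20-point target and an SE near 5. This rests on assumed correlations and an assumed late share, and the clash at Day 117 rests on a Day 112 last dose. Two smaller routes were not quantified: covariates entered without a visit interaction (and their selection), and the change in dimension of the inverse-Wishart prior.

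Correction is still worthwhile, because the plan should determine one primary data set and state its departures from the protocol.

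**What to change.** - **SAP 9.4.3 and 9.2:** fit the primary MMRM and the covariate selection to the protocol's six visits. Report Week 20 from a separate model or as a summary.
- **If seven visits are kept:** set Week 20 to missing wherever Table 3 sets Week 16 to missing, list the change in Table 8, and run the six-visit model as a check.
- **SAP 7.7:** add an exception for PASI scores that Table 3 sets to missing, so that one rule governs.
- **Reporting:** tabulate by arm how many completers lose their Week 16 score, since the documents give no basis for predicting this.

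The cost is SAP wording, one extra model for Week 20, and an SE increase of 2% or less in the cases computed.

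### The completer-versus-discontinuer plot cannot test missing at random, yet the SAP lets such diagnostics lead to a change of primary model after unblinding

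*SAP*

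**What the plan says.** Protocol Section 7 sets the assumption: "missing data will be considered as missing at random and will be accounted for using mixed models for repeated measures". It extends this to scores excluded because they were collected after treatment discontinuation. SAP Table 3 makes that exclusion concrete for the primary estimand: PASI scores taken more than 4 days after stopping treatment are set to missing up to Week 16.

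SAP 9.4.3 then gives the check: "The assumption that data are missing at random will be evaluated by plotting the mean percentage change in PASI score against visit". Within each arm, the figure sets those who finished their 16 weeks of dosing against those who stopped early. Protocol 7.6.1 has the same check. The figure (14.2.1.5 in SAP 15.2.2) uses the primary-estimand data and is also an interim output.

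The consequence follows in SAP 9.4.3: "If model checking and diagnostic plots show a violation of the assumptions underlying the analysis, alternative statistical methods will be considered". The listed options are dropping covariates, or "using an appropriate transformation (e.g. logarithmic) on the endpoint or changing the modelling strategy from MMRM". On timing: "Requirements for alternative methods will be data driven and cannot be fully assessed until after the study has been unblinded and this document finalised". Any change is to be described in a SAP addendum.

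SAP Table 4 fixes three supportive estimands in advance. Number 2 is treatment policy and uses scores collected after discontinuation. Number 3 carries the worst on-treatment score forward for participants who stop because they need another therapy.

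**The concern.** MAR is a statement about scores nobody saw, given the scores that were seen. The plot compares only scores that were seen, and Table 3 has removed most post-discontinuation values from it. If discontinuers were doing worse before they stopped, the curves separate. That argues against missing completely at random, not against MAR, and a likelihood-based or Bayesian MMRM is used precisely because it accommodates such differences. If instead participants stop because of what was about to happen to their skin, the curves may barely differ although MAR is false.

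Two things are at stake. First, the primary Week 16 difference rests on MAR for participants who stop, and no planned analysis shows how far the result depends on it. Second, a visible gap could be taken as a violation and used to justify another primary model when treatment codes are known. The section gives no criterion for a violation, no fallback model, no decision-maker, and no statement that the MMRM result will still be reported as primary.

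**Working it through.** **1. Inputs from the documents** (Protocol 7.3, SAP Section 6): SD 25 points; target difference 20 points; at most 15% discontinuing before Week 16; 42 evaluable per active dose and 21 placebo per cohort, so 63 pooled placebo.

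**2. The plan's own power figures.** SE of a difference = SD × √(1/n₁ + 1/n₂).
- Pooled: 25 × √(1/42 + 1/63) = 4.98 points. Two-sided 5% power = Φ(20/4.98 − 1.96) = 98.0% (97.8% with the noncentral t). The stated figure of more than 95% reproduces.
- Within cohort: 25 × √(1/42 + 1/21) = 6.68 points. Power = 84.9% (83.8% with the noncentral t). The stated figure of more than 80% reproduces.

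The power statement is not in dispute. The SE of about 5 points is the yardstick used below.

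**3. What the plot can show.** MAR requires P(dropout | seen, unseen scores) = P(dropout | seen scores). The plot estimates mean seen score among discontinuers minus mean seen score among completers. MAR does not restrict that quantity; only missing completely at random makes it zero.

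**4. Simulation.** Six visits (Weeks 1, 2, 4, 8, 12, 16), SD 25, dropout set to 15%. Assumed, because the documents give no values: true Week 16 mean −30 (placebo −10 plus effect −20); first-order autoregressive correlation between successive visits of 0.5 to 0.9; dropout log-odds slope of 0.6 to 1.8 per SD. Each setting used 300,000 participants in one arm. Sequential-regression maximum likelihood for monotone dropout stood in for the MMRM. Under MAR, dropout depends on the last seen score. Under MNAR (not at random), it depends on the part of the next, unseen score that the previous score does not predict. Gap is discontinuers minus completers over Weeks 2 to 12; bias is estimated minus true Week 16 arm mean.

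| Correlation | Slope | MAR: gap | MAR: bias | MNAR: gap | MNAR: bias |
|---|---|---|---|---|---|
| 0.5 | 0.6 | 7.4 to 14.8 | 0.00 | −0.3 to −0.1 | −0.93 |
| 0.5 | 1.2 | 13.5 to 27.3 | −0.03 | −0.4 to 0.1 | −1.81 |
| 0.5 | 1.8 | 17.6 to 36.1 | 0.01 | −0.1 to 0.1 | −2.39 |
| 0.7 | 0.6 | 9.7 to 15.1 | 0.01 | −0.2 to 0.1 | −1.05 |
| 0.7 | 1.2 | 17.9 to 26.6 | 0.01 | −0.2 to −0.1 | −2.00 |
| 0.7 | 1.8 | 23.1 to 35.0 | 0.03 | −0.1 to 0.0 | −2.69 |
| 0.9 | 0.6 | 13.1 to 14.4 | 0.00 | 0.0 to 0.1 | −0.91 |
| 0.9 | 1.2 | 23.7 to 25.0 | −0.01 | −0.4 to 0.2 | −1.67 |
| 0.9 | 1.8 | 29.6 to 31.7 | −0.01 | −0.2 to 0.1 | −2.22 |

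A separate simulation (correlation 0.8, SD rising from 12 to 25, 13–14% dropout) agrees. Under MAR the gaps were 8 to 21 points at Weeks 1 to 8, with an estimate of −19.9 against a true −20.0. With dropout driven by the unseen next change, the gaps were −1 to −5 points, with an estimate of −21.9 against −20.1.

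**5. Effect on the treatment difference** (correlation 0.7, slope 1.2). MNAR in both arms: estimate −20.02 against a true −20.02, so the arm biases cancel. MNAR in the active arm only, with completely random dropout on placebo: estimate −22.05 against a true −20, an error of about 2 points, or 2/4.98 ≈ 0.4 SE.

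**6. Noise in the plot.** 15% of 50 is 7.5, say 8 discontinuers per active arm against 42 completers. If SD 25 applies and all 8 are still observed, the SE of one gap is 25 × √(1/8 + 1/42) = 9.6 points.

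**7. The log option.** The endpoint is 100 × (PASI at visit − baseline)/baseline. It is negative for every improved participant, so its log cannot be taken. Log(PASI at visit/baseline) = log(1 + percent change/100) is defined except at PASI = 0, where it needs an offset.

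**The case against.** The best defence has four parts.

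- **Discontinuation is examined elsewhere.** A reader might infer that the plan has no other look at it. That is not so. Supportive Estimand 2 uses actual scores after stopping, Protocol 4.2.1 encourages participants who stop to keep attending, and Supportive Estimand 3 imposes a poor outcome on those needing other therapy. What remains is that both target different estimands, and neither varies MAR for the primary one.
- **The switching clause is qualified.** A reader might infer that the sponsor may replace the model at will. The SAP says alternatives will be considered, should suit the violation seen, and must be documented; it names no decision-maker; and the plot is one diagnostic among several. This stands, but an addendum records a change made with codes known and does not prevent it. The trial tests no formal hypothesis, which limits type I error concerns but not selection of the reported estimate.
- **The bias is small.** A reader might set 2 points against the 20-point target and call it a 10% error. The table gives the bias in one arm's mean, whereas the target is a between-arm difference; the bias carries over in full only if the mechanism acts in one arm.
- **The log can be made to work.** A reader might infer that it is impossible here. The ratio form is workable with an offset, and SAP 9.4.4 already uses one for log dose. What is missing is a definition.

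**Conclusion.** The point holds. The plot cannot do the job that SAP 9.4.3 and Protocol 7.6.1 give it: it can show a large gap when MAR is true and almost none when MAR is false. That conclusion follows from the definition of MAR. The simulated sizes are illustrative and rest on the assumed correlation and dropout slope: separation of about 7 to 36 points with no bias under MAR, and an arm-mean bias of about 1 to 3 points with little visible gap under MNAR, against an SE of about 5 points for the treatment difference.

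The documents do not show that the primary result will be biased or that a model switch is intended. The defect is that a non-diagnostic plot is among the triggers for an open-ended choice of primary model after unblinding, and that the sensitivity of the primary estimand to MAR is left unexamined. This should be corrected, but it does not undermine the design.

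**What to change.** 1. In SAP 9.4.3, and in Protocol 7.6.1 at the next amendment, call the plot descriptive and remove the statement that it evaluates MAR.
2. State that the prespecified Bayesian MMRM remains the reported primary analysis whatever the diagnostics show. Run residual checks on treatment-masked data before unblinding. Report any alternative model beside the MMRM as a sensitivity analysis.
3. Add a prespecified delta-adjusted (tipping-point) analysis of the primary estimand. In the active arms, shift Week 16 scores missing because of treatment discontinuation towards worse by a stated range, for example 0 to 30 points, with the reason for the range given. Report the treatment difference and P(difference < 0) at each value. Exclude treatment completers whose Week 16 score is missing only because the visit fell more than 4 days after the end of treatment (footnote to SAP Table 3). With 15% missing for discontinuation, a shift of 30 moves the active mean by 0.15 × 30 = 4.5 points, about 0.9 SE, so the range is informative without being extreme.
4. Either define the log option as log(PASI at visit/baseline) with a stated offset for PASI = 0, or delete it.

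The cost is SAP wording, a few lines of code on the existing posterior draws, and a few extra outputs. Nothing in the design or conduct of the trial changes.
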